Immunomodulatory effect of **p**leuran (β-glucan from *Pleurotus ostreatus*) in children with recurrent **r**espiratory **t**ract **i**nfections

IPRRTI study

Study Protocol

NCT number: NA

Basic information about the study

Title of the study:	Immunomodulatory effect of pleuran (β -glucan from Pleurotus ostreatus) in children with recurrent respiratory tract infections (RRTI).				
Study abbreviation:	IPRRTI				
Principal investigator and site:					
Co-investigators and sites:					
Study design:	Multicenter, prospective, randomized, double-blind, placebo-controlled study with a food supplement.				
Study population:	250 patients aged 3-18 years enrolled by investigators at 36 centers, randomized to the active and placebo groups (1:1 ratio)				
Primary endpoints:	 To evaluate the effect of pleuran administration (Imunoglukan P4H[®] chewable tablets) compared to the placebo group on: reduction in the number of RTIs episodes (total number) 				
Secondary endpoints:	 To evaluate the effect of pleuran administration (Imunoglukan P4H[®] chewable tablets) compared to the placebo group on: reduction in the number of episodes of RTI subtypes reduction in the duration of RTI episodes (total duration, RTI subtypes) reduction of the need for antibiotic (ATB) therapy reduction of the number of missed days at school/nursery due to RTI reduction of the number of missed working days due to RTIs reduction of the number of emergency department visits due to RTI reduction of the number of physician visits due to RTI 				

Timeline

Pre-screening of patients: July-September 2023 **Date of enrolment of the first patient:** 15.09.2023 **Date of enrolment of the last patient:** 31.12.2023 **Study completion date:** 31.03.2024 **Study duration and visit plan:** 3 months, 4 visits in total: VO - initial visit, V1 - control visit after 30 ± 7 days from enrolment, V2 - control visit after 60 ± 7 days from enrolment and V3 - control visit after 90 ± 14 days from enrolment (completion).

Introduction

Respiratory tract infections (RTIs) are the most common cause of morbidity at every age category, especially in childhood. At the same time, they are also the most common cause of consultations and visits in clinical practice of every pediatrician. Upper respiratory tract infections have a higher prevalence, and about 10-30% of patients develop lower respiratory tract infections. The most common cause are viruses (90-95%).

Respiratory infections are characterized by both microbial load, respiratory epithelium response, and activation of inflammation and immune responses. These aspects lead to structural and functional changes in the respiratory tract. There is an overgrowth of goblet-shaped glands, which leads to excessive production of hyperviscous mucus. There is a weakening of mucociliary clearance, either due to the direct toxic influence of microorganisms on cilia and their oscillation, but also indirectly through an increase in the viscosity of mucus in the lumen of the respiratory tract. Respiratory epithelial cells form many pro-inflammatory and chemotactic compounds that lead to the development of inflammatory infiltrate in the airways. This is accompanied by oxidative stress, which impairs both the structure and function of biomolecules. Inflammation subsequently increases the reactivity of cough receptors. All these factors cause clinical signs of respiratory infections, whether from the respiratory tract (cough, expectoration, obstruction with wheezing, bronchial hyperreactivity, congestion and runny nose) or at the level of the whole organism (increased body temperature, weakness, myalgia and fatigue).

Recurrent respiratory tract infections (RRTIs)

RRTIs are a separate category of RTIs and represent a typical medical problem of preschool and school age. They can be defined on the basis of several aspects as infectious respiratory diseases, in which other more serious causes have been excluded (cystic fibrosis, primary immune disorders, congenital ciliary dyskinesias, respiratory malformations). Most children with RRTIs do not suffer from severe immunodeficiency and the high frequency of respiratory infections is due to a combination of various factors (immaturity of the immune system, high exposure to infectious agents in the family or children's collective, environmental factors, adenoid hypertrophy, etc.). In addition, allergic inflammation in the airways may also contribute to increased susceptibility to RTIs.

According to data from epidemiological studies, approximately 6-10% of children between 2-6 years of age suffer from RRTIs. Due to their high incidence, RRTIs have an important socio-economic impact (affecting quality of life, missed school days, missed days at work, repeated medical examinations, hospitalization, as well as increased antibiotic prescription).

However, it is equally important to define what the term RRTIs means, as the parent's opinion and a doctor's point of view can differ significantly. When assessing RRTIs, in addition to their frequency, their course, duration, response to pharmacological treatment, cultivation of the pathogen as well as the development of complications are much more important. At the same time, the so-called "physiological morbidity of the child" must also be taken into account, which is considered to be:

- Children 3-5 years: 6 8 RTIs with mild course, good response to treatment, predominantly during the autumn and winter months
- **Children 6-12 years:** 2 4 RTIs with mild course, good response to treatment, predominantly during the autumn and winter months

The treatment of RRTIs consists not only from the treatment of each infection, but should be mainly aimed at their prevention. Therapeutic and preventive strategies should aim to support weakened immune system functions, e.g. by **immunomodulation**. Immunomodulation can be defined as therapeutic or preventive intervention in the activity of the immune system in order to achieve homeostasis.

In practice, various preparations of natural origin are used to prevent RRTIs, but only few of them have scientific evidence proving efficacy with a sufficient number of relevant clinical studies and observations that elucidate individual aspects of the mechanisms of action as well as proven efficacy and safety in the management of individual diseases. Vitamins, minerals, as well as many natural immunomodulatory preparations (phytotherapy, probiotics, prebiotics, biologically active polysaccharides) are most commonly used, while individual biological effects are important – anti-infectious, immunomodulatory, anti-inflammatory, antioxidant, etc. By using these preparations or their combination, a synergy of effects can be obtained in the treatment of the selected condition.

Biologically active polysaccharides (BAP e.g., β -glucans - polymers of glucose commonly found in fungi, yeast, bacteria and cereals) represent one of the most studied natural immunomodulators with pluripotent biological effects (anti-infectious, antiviral, immunomodulatory). Selected molecules have an anti-inflammatory effect, inhibit the production of pro-inflammatory cytokines, and their preventing effect on lung damage was described in an animal model. By promoting the production of anti-inflammatory and regulatory substances, they restore balance in the cytokine network. The antiviral effect of BAP can be mediated either directly, through inhibition and/or disruption of viral particle integrity, or indirectly, by enhancing host antiviral defenses by supporting the body's immune processes. Other significant effects of β -glucans include their significant immunomodulatory effect (increasing the number of NK cells, stimulating phagocytic activity, promoting the development of antibody production, improving the post-vaccination response) and modulating effect on T-lymphocytes. The mechanism of action of β -glucans is mediated by several receptors, the most important is the Dectin-1 receptor.

Zinc application may also have a possible positive effect on the immune system, as several studies have suggested its effect in coronavirus infections. In vitro, zinc inhibits RNA-polymerase activity as well as virion replication. Vitamin D is also important for the functioning of the immune system, its positive effect has been observed in protection against infections (antibacterial effect, anti-inflammatory effect, differentiation of monocytes into macrophages), tumor diseases (anti-proliferative and antidifferentiation effect), and its deficiency may be a risk factor in the development of immunopathological reactions (autoimmune diseases).

The efficacy and safety of food supplement Imunoglukan P4H[®] (pleuran, β -glucan from *Pleurotus ostreatus*, enriched with vitamin C) has been proven in numerous clinical studies and observations in children and adults, and it is therefore a suitable choice for supporting weakened immunity for both short-term and long-term use. Open-label and double-blind, placebo-controlled studies in children with recurrent respiratory infections confirmed the preventive effect of Imunoglukan P4H[®] on the incidence and intensity of recurrent bacterial and viral infections in children from 1 year of age. Imunoglukan P4H[®] has also shown the ability to induce changes in specific and non-specific cellular immunity parameters, which have reflected into a reduced incidence of respiratory infections in children and adults, prevention of immunosuppression induced by intense physical stress, and reduction of the incidence of infectious exacerbations in patients with chronic inflammatory diseases.

Supplementation with Imunoglukan P4H[®] was also able to achieve significant changes in markers of allergic inflammation in children (total IgE, blood eosinophil count), thus confirming previous results of in vitro tests, which indicated the anti-allergic potential of this active substance. Taking Imunoglukan P4H[®] supports physiological functions and maturation of the immune system in children and does not

cause its overstimulation. Imunoglukan P4H[®] ACUTE! (pleuran + vitamin C + zinc) confirmed its immunomodulatory effect in shortening the duration of symptoms in patients with herpes simplex virus type 1 (HSV-1) infection.

The results of clinical studies have confirmed the complex immunomodulatory effect of this preparation without any significant side effects.

Study design

It is a multicenter, prospective, randomized, double-blind, placebo-controlled study with a food supplement at an outpatient healthcare provider.

The investigators will enroll a total of **250 patients** who meet the inclusion criteria. The proposed study does not imply any change in pharmacological/non-pharmacological treatment, diagnostic interventions administered to enrolled subjects. In case the respiratory tract infections occur during the study period, the patient enrolled in the study will be treated according to standard management plan.

Patients will be randomized into 2 arms (active group and placebo group):

- Active group: Imunoglukan P4H[®] chewable tablets (IMG[®] 50 mg + Zinc 5 mg + Vitamin D 10 μg in 1 tablet):
 - up to 25 kg of body weight 1 tablet once a day for 3 months
 - over 25 kg 2 tablets once a day for 3 months
 - Placebo group: Placebo chewable tablets (Zinc 5 mg + Vitamin D 10 μ g in 1 tablet)
 - o up to 25 kg of body weight 1 tablet once a day for 3 months
 - o over 25 kg 2 tablets once a day for 3 months

Discussion about design

Multicenter, prospective, randomized, double-blind, placebo-controlled study design is a perpective for obtaining clinically, scientifically and statistically significant results to elucidate the impact of the investigational product on primary and secondary endpoints. The 3-month duration of the study is justified in evaluating the modulation of the immune response and its clinical impact on such events as a reduction in the number of respiratory infections, shortening their duration, and reducing the need for ATB treatment. In addition to confirming the underlying hypothesis, the pilot study should also provide data on tolerability, safety and possible adverse effects.

Subjects enrolled in the study complete an anamnestic data collection and fill out relevant questionnaires during control visits.

Study endpoints

Primary endpoints – to evaluate the effect of pleuran administration (Imunoglukan P4H[®] chewable tablets) compared to the placebo group on reduction in the number of RTIs episodes (total number)

Secondary endpoints – to evaluate the effect of pleuran administration (Imunoglukan P4H[®] chewable tablets) compared to the placebo group on:

- reduction in the number of episodes of RTI subtypes
- reduction in the duration of RTI episodes (total duration, RTI subtypes)
- reduction of the need for antibiotic (ATB) therapy
- reduction of the number of missed days at school/nursery due to RTI
- reduction of the number of missed working days due to RTIs
- reduction of the number of emergency department visits due to RTI
- reduction of the number of physician visits due to RTI
- tolerability and safety

Inclusion criteria

- signed informed consent
- age 3-18 years
- history of recurrent respiratory infections:
 - Age 3 to 5 years (< 6 years): 6 or more upper or lower respiratory tract infections from October 2022 until the end of March 2023
 - Ages 6 to 18 years (≥ 6 years): more than 3 upper or lower respiratory tract infections from October 2022 until the end of March 2023

Exclusion criteria

- refused informed consent
- bronchopulmonary dysplasia
- primary immunodeficiency
- cystic fibrosis
- chronic diarrhoea
- chronic diseases of the lungs, kidneys and liver
- malformations of the cardiovascular system
- oncological disease
- malnutrition
- intolerance to any of the ingredients in the study product
- taking preventive immunomodulatory therapy (beta-glucans, bacterial lysates, isoprinosine) less than 14 days prior enrolling the patient into the study

List of data collected from study subjects

Basic identification data	• Patient ID				
	 Patient Initials 				
	 Patient's Date of birth 				
	 Date of completion of CRF / Date of visit 				
Medical history and	o Age				
demographics	o Sex				
	 Current comorbidities 				
	 Current treatment of comorbidities 				
Diagnostic procedures	 Patient diary (Respiratory infections) 				
Primary endpoints	 RTIs incidence (total) 				
Secondary endpoints	 RTIs subtypes incidence 				
	 Duration of RTIs (total duration, RTIs subtypes) 				
	 The need for ATB therapy for the treatment of RTIs 				

	0	Number of missed days in school/nursery due to RTIs		
	0	Number of missed working days due to RTIs of the child		
	• Number of Emergency department visits due to			
	0	Number of Physician visits due to RTIs		
	0	Tolerability		
	0	Safety (occurrence of adverse events)		
Other data	0	Compliance		

Study visit and evaluation plan

Visit number	V0	V1	V2	V3
Day of visit	Initial	after 1 st month	after 2 nd month	after 3 rd month
	examination	(30 ±7 days)	(60 ±7 days)	(90 ±14 days)
Informed consent	Х			
Inclusion / exclusion	х			
criteria				
Demographics	Х			
Medical history	х			
Comorbidities	х	х	Х	х
Dispensing of study product	Х			
Incidence of respiratory tract infections (Patient diary)		Х	Х	х
Adverse events		Х	х	х
Returning the study product, product accountability and patient compliance				х

Required diagnostic procedures

Patient diary "Respiratory tract infections"

Parents or legal representatives of study subjects will record up-to-date data (incidence of infectious morbidity, symptoms, need for ATB therapy, physician or emergency department visits, number of missed days at school/nursery and work due to RTIs) throughout the study period. The filled "Patient diary" will be handed over to the treating physician at each visit.

Adverse event form

The physician fills out the Adverse event form when adverse events occur and records the occurrence of adverse events also in the CRF.

Compliance

Study subjects will return the container with remaining study medication at V3 (visit after 3 months) to their treating physician, who will count the number of remaining tablets. The physician will record the result in CRF. Patients with <75% compliance will be excluded from the study due to lack of collaboration.

Appendices to the study protocol, other changes in the conduct of study

Any amendments to the Protocol will be made in the form of an Appendix to the Protocol. Changes to the study are not permitted. Any unexpected and sudden changes in the conduct of study will be recorded in the clinical report.

Privacy Policy

All patients in this study will be identified with a unique ID. Identification of the patient through this ID will not be possible. Only the monitor can validate the source data. The unique ID of a particular patient will only be known to the investigator or monitor. The personal identification data entered into this study will be: date of birth, gender and initials. The nature of personal data identifiers is governed by all relevant legislative requirements.

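### Does the completion date of 31.03.2024 leave too little time for the V3 visit of children enrolled in late December 2023?

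*Combined protocol and SAP*

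**What the plan says.** The Timeline sets the calendar with three dates: "Date of enrolment of the first patient: 15.09.2023", followed by "Date of enrolment of the last patient: 31.12.2023 Study completion date: 31.03.2024". Each child's participation is given there as "3 months, 4 visits in total", ending with "V3 - control visit after 90 ± 14 days from enrolment (completion". The table under Study visit and evaluation plan repeats the same V3 window. Study design gives supplementation the same length; for the lower weight band it reads "1 tablet once a day for 3 months".

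V3 carries data that no other visit collects. Under Compliance, "Study subjects will return the container with remaining study medication at V3 (visit after 3 months) to their treating physician", and children below 75% compliance are excluded. Under Required diagnostic procedures, the diary is handed over at every visit, so the part covering the time after V2 arrives at V3.

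The protocol does not say whether 31.03.2024 is a planned date or a hard cut-off, nor what happens to a V3 held after it.

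**The concern.** The protocol labels V3 as completion, so one expects the study to complete no earlier than the last permitted V3. It does not: the late edge of the last child's window lies in mid-April. The completion date looks as if it was set from the nominal three months with the tolerance left out.

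If sites treated 31.03.2024 as a hard stop, a late enrollee whose V3 slipped within the allowed window could lose that visit. The final diary segment would go with it, about a third of the follow-up for the primary endpoint (day 60 to day 90 of 90 days). So would the only tablet count, and without it the child could not be classified under the 75% rule. If illness at the end of follow-up were what delayed the visit, the missing data would be related to the outcome. It would also fall on children followed from January to March.

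**Working it through.** **Inputs, all from the Timeline.** First enrolment 15.09.2023; last enrolment 31.12.2023; completion 31.03.2024; V3 at 90 ± 14 days, that is, day 76 to day 104; 250 children (Basic information about the study). 2024 is a leap year.

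**The plan's own date.** 31.12.2023 + 3 calendar months = 31.03.2024, an exact match. In days: 31 (January) + 29 (February) + 31 (March) = 91.

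**Window of the last child (enrolled 31.12.2023).**

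| Day | Date | Relative to 31.03.2024 |
|---|---|---|
| 76, window opens | 16.03.2024 | 15 days before |
| 90, target | 30.03.2024 | 1 day before |
| 104, window closes | 13.04.2024 | 13 days after |

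This child can have V3 on any of 16 calendar days (16 to 31 March) inside both the window and the study period. By the calendar, 30 and 31.03.2024 are a Saturday and a Sunday, so 10 of the 16 are weekdays (18 to 22 and 25 to 29 March).

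**Who is affected.** Latest enrolment with the full window: 31.03.2024 − 104 days = 18.12.2023. Enrolments from 19.12 (window closes 01.04.2024) to 31.12.2023 have it trimmed by 1 to 13 days, on average (1 + 13)/2 = 7. If enrolment is counted as day 1, the cut-off moves by one day, to 19.12.2023.

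**Who can reach the target.** Latest enrolment with day 90 on or before completion: 31.03.2024 − 90 days = 01.01.2024. That covers every child.

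**Number with a trimmed window.** 15.09 to 31.12.2023 inclusive is 108 days, and 13/108 = 12.0%. With even enrolment (assumed), 0.120 × 250 = 30 children.

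**Number whose V3 would fall after 31.03.2024.** As an illustration, assume that V3 dates are uniform over the 29 window days (76 to 104) and that sites make no effort to book earlier. The average chance for a trimmed child is 7/29 = 24%.

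| Enrolment rate, 19 to 31.12 (assumed) | Trimmed | V3 after 31.03.2024 | Share of 250 |
|---|---|---|---|
| Half the even rate | 15 | 3.6 | 1.5% |
| Even | 30 | 7.3 | 2.9% |
| Twice the even rate | 60 | 14.5 | 5.8% |

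If V3 is booked at or before day 90 and kept, the number is zero. Even the visits in the table are lost only if data collected in April are refused.

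**The case for a change.** The strongest case for acting is that the slack is thin where it is needed. For the 31.12.2023 enrollee, the target day and the single later day both fall on a weekend, and the study runs in outpatient care. A child enrolled on Friday 29.12.2023 reaches day 90 on Thursday 28.03.2024 and has one weekday of late allowance left. The section on appendices and changes in conduct says that changes to the study are not permitted, so a site might feel unable to treat the date as soft. V3 is the only source of the tablet count, and the protocol gives no rule for a missing one. The remedy would be one line.

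The arithmetic in that case stands, and so does the observation that the protocol leaves the status of the date open. The step to lost or biased data does not.

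- The early half of the window is untouched for every child, so a site that knows the calendar has two weeks before the target in which to book.
- The same section allows amendments by appendix and has unexpected changes in conduct recorded in the clinical report. It does not tell anyone to discard an in-window visit.
- The documents do not support the idea that illness delays V3. V3 takes place with the treating physician, whom a sick child may be seeing anyway.
- Allocation is randomised 1:1, so late-December enrolment and winter season should be shared by both arms. No mechanism for a difference between arms is apparent.
- Diaries handed over at V1 and V2 are safe in any case.

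Closing enrolment on 18.12.2023 instead would give up 12% of the recruitment period to protect a tolerance.

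**Conclusion.** This is a small scheduling inconsistency, and no change to the plan follows. For enrolments from 19.12 to 31.12.2023 the late side of the V3 window runs 1 to 13 days past the stated completion date. Three months of follow-up and the day-90 visit fit for every child, and the completion date agrees with the planned duration.

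About 30 of 250 children (even enrolment assumed) have part of a tolerance trimmed. The number who would lose V3 is zero unless two conditions hold together: the visit runs late, and 31.03.2024 is enforced as a cut-off. The protocol does not state the second. A study team would sensibly read the date as the nominal last visit and accept an in-window V3 in early April. On that reading the analysis set, the primary episode count and the compliance classification are unaffected.

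The conclusion rests on reading the 14 days as a visit tolerance, which is how the Timeline and the visit table present them. It would need another look only if the sponsor intended to close data collection on 31.03.2024 regardless of the window.

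### Nothing keeps siblings out of opposite arms, and no household identifier is collected, so tablet mixing and shared infections at home could dilute the RTI comparison

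*Combined protocol and SAP*

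**What the plan says.** - **Unit of allocation.** The basic information table plans "250 patients aged 3-18 years enrolled by investigators at 36 centers, randomized to the active and placebo groups (1:1 ratio"). The Study design section repeats that "Patients will be randomized into 2 arms (active group and placebo group"). No allocation method, stratification or sibling rule is given.
- **Eligibility.** The age range of 3-18 years is wide enough for brothers and sisters. Apart from consent, the exclusion criteria concern medical conditions, intolerance and recent treatment, the last being "taking preventive immunomodulatory therapy (beta-glucans, bacterial lysates, isoprinosine) less than 14 days prior enrolling the patient into the study". None concerns another child in the household.
- **Setting and disease.** The design is described thus: "It is a multicenter, prospective, randomized, double-blind, placebo-controlled study with a food supplement at an outpatient healthcare provider". The background section on RRTIs lists "high exposure to infectious agents in the family or children's collective" among the reasons for frequent infections.
- **Product.** Both arms receive chewable tablets. The comparator is listed as "Placebo chewable tablets (Zinc 5 mg + Vitamin D 10" µg), so it shares the zinc and vitamin D of the active tablet. Children up to 25 kg take one tablet a day and heavier children two.
- **Accountability.** Under Compliance, the container is returned at V3 to the physician, "who will count the number of remaining tablets". The visit plan schedules no earlier count.
- **Data collected.** The list of data has patient ID, initials and date of birth, but no household identifier. Missed work is listed as "Number of missed working days due to RTIs of the child".

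**The concern.** Children in one family share exposure and often share a doctor, so two siblings with recurrent infections could both qualify at the same practice. The protocol neither prevents this nor says what happens next. If the two are allocated to different arms, three things follow.

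1. Two containers of double-blind chewable tablets are in one home, and doses can be mixed. The compliance check counts tablets; it does not show which child took them.
2. RTIs spread within the home. If the product prevents infections, the placebo sibling gains some protection from the active sibling, and the active sibling stays exposed to the placebo sibling's infections. One child's allocation then affects the other's primary outcome.
3. The siblings' outcomes are correlated, including a parent's missed working days. With no household identifier, the sponsor could not reliably find these pairs and allow for that.

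The first two shrink a true difference on the primary endpoint. The third affects its precision.

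**Working it through.** **Is the gap there?** The inclusion and exclusion criteria, Study design, the data list, the visit plan and Compliance contain no household limit, no sibling allocation rule and no household field. The plan's total of 250 cannot be reproduced, because the protocol gives no alpha, power, effect size, event rate or dropout for it.

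**What can the V3 count detect?** If two siblings exchange tablets one for one, each container loses the same number as under correct use, so both counts are unchanged and the 75% compliance threshold is not triggered. If they swap whole containers and take different daily numbers of tablets (one below and one above 25 kg), the containers empty at the wrong rates and the count could show it. Within one weight band, even a whole-container swap is invisible.

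**How large might the dilution be?** From the protocol: 250 children, 1:1, so n = 125 per arm. Everything else is assumed:
- share of children in enrolled sibling pairs, s = 5% to 20%;
- half of the pairs split, as under independent 1:1 allocation;
- share of doses mixed in split homes, w = 25% to 50%, where 50% means the two children's treatments no longer differ;
- true rate ratio R = 0.70; placebo mean 1.5 RTIs over the study; negative binomial shape 2; two-sided alpha 0.05.

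Children in split homes: 250 × s/2, which is 6.25 at s = 5% and 25 at s = 20%.

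Mean RTI count relative to unmixed placebo:
- active = (1 − s/2)·R + (s/2)·[1 − (1 − w)(1 − R)]
- placebo = (1 − s/2) + (s/2)·[1 − w(1 − R)]

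The observed rate ratio is active/placebo. The variance of its log is (1/μ_placebo + 1/μ_active + 2/shape)/n, and power is Φ(|log ratio|/SE − 1.96).

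*No mixing.* Means 1.5 and 1.05. Variance (0.6667 + 0.9524 + 1)/125 = 0.02095, SE 0.1447. |log 0.70| = 0.3567, z = 2.464, power Φ(0.504) = 69%.

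*Low end (s = 5%, w = 25%).*
- Active: 0.975 × 0.70 + 0.025 × 0.775 = 0.7019.
- Placebo: 0.975 + 0.025 × 0.925 = 0.9981.
- Ratio 0.703, z = 2.433, power 68%.

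*High end (s = 20%, w = 50%).*
- Active: 0.90 × 0.70 + 0.10 × 0.85 = 0.715.
- Placebo: 0.90 + 0.10 × 0.85 = 0.985.
- Ratio 0.726, z = 2.217, power 60%.

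| s | w | Observed ratio | Power |
|---|---|---|---|
| none | – | 0.700 | 69% |
| 5% | 25% | 0.703 | 68% |
| 5% | 50% | 0.706 | 67% |
| 20% | 25% | 0.713 | 65% |
| 20% | 50% | 0.726 | 60% |

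**Cross-check with a different model.** Take a comparison of means with an assumed 80% power at 125 per arm (standardised effect 0.354). The effect is multiplied by 1 − (s/2)·2w, which is 0.988 at the low end and 0.90 at the high end. Power becomes 79% and 71%. Restoring it would need 250/multiplier², or 257 and 309 children. The direction and size agree.

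Transmission between siblings is not in these figures; the documents give nothing from which to estimate it.

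**The case against.** The strongest reply is that the problem may hardly arise. Both siblings must meet a strict history: at least 6 infections in one October-March season if under 6 years, more than 3 if older. The background puts RRTI at about 6-10% of children aged 2-6, although shared exposure would raise the chance that siblings both qualify. Centres average about 7 children (250/36). The high end of the range needs 25 enrolled pairs and complete loss of the treatment distinction in every split home, and nothing in the documents supports either. That stands: the upper figure is a bound under assumptions, not an expectation, and at the low end the loss is about one percentage point of power.

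A reader might also infer more than the protocol supports:
- *That the tablets are indistinguishable.* Double-blinding makes this a fair inference, but appearance, taste and labelling are not described.
- *That any swap goes unnoticed.* This holds for one-for-one exchange or within a weight band, not for every swap.
- *That siblings are split half the time.* This assumes independent 1:1 allocation; the method is not given, and blocking within centres would change the figure.
- *That siblings' data will be analysed as independent.* There is no analysis section. The supportable statement is that no handling is specified.
- *That one parent's day at home is wrongly counted twice.* The endpoint is defined per child. A day lost because two children were ill can be attributed to each, and the diary form is not shown. What remains is correlation within the household, not a counting error.

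None of this supplies the missing rule.

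**Conclusion.** The concern holds as a gap in eligibility and data collection. Nothing in the protocol prevents siblings from entering opposite arms, nothing would identify them afterwards, and the one compliance check cannot reveal a one-for-one exchange. If the product has an effect, both mixing and within-home spread bias the RTI comparison toward no difference.

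The size is unknown. The illustrative loss of 1 to 9 percentage points of power rests wholly on the assumed sibling share, splitting, mixing, rate ratio and count distribution, and it leaves out transmission. This is a cheap improvement that protects the primary contrast. It does not show that the trial is compromised, or that any siblings were in fact enrolled.

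**What to change.** Add one line to the exclusion criteria: *another child of the same household already enrolled in this study*. This removes cross-arm tablet mixing, interference between siblings and household correlation together. The cost is the second child in a few families.

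If siblings have already been enrolled, add a household ID to the CRF, use household-robust standard errors for the RTI count and the secondary endpoints, and report how many pairs were split. This costs one field and a variance option. It deals with the correlation but cannot undo any mixing or transmission that has occurred. Keep missed working days as the per-child endpoint the protocol defines; counting them once per household would change the endpoint.
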